Oxytocin: The oxytocin and oxytocin-matched placebo will be formulated at 5mg/0.1mL (5mg/spray) and dispensed as 10-mL nasal spray, twice a day (2 sprays per nostril) for 7 days (total daily dose: 40 international units, IU). Previous pilot studies have demonstrated that oxytocin administered either as single dose (73) or daily for two weeks (72) was well-tolerated in individuals with co-occurring opioid and cocaine disorder. The intranasal dose was chosen based on earlier work (102, 103) and previous studies (69, 104) have shown that 40 IU is well-tolerated in healthy populations with minimal to no side effects or adverse events. The administration period (7 days) is within the confines of an acceptable timeframe based on previous studies and ongoing oxytocin clinical trials (NCT: 02407340 and NCT: 02548728). A study conducted by the PI's mentor, [name] and his team (105), indicated that both intranasal and intravenous exogenous (labelled) oxytocin cross the blood brain barrier and reach the CSF in rhesus macagues (106). As most of the neurohypophysial hormones, oxytocin has very short half-life, however, the pharmacological effect of oxytocin may extend from the transient kinetic effects. Intranasal oxytocin has shown to blunt stress effects on hippocampal synaptic plasticity and memory in rats via acting on oxytocin receptors and regulating phosphorylated extracellular signal-regulated kinases (pERK)(107). As such, oxytocin may induce compensatory mechanisms regulating secretion of magnocellular neurons in the hypothalamus which are operant on other hormones (108).

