Visit 3 (Laboratory Session I) – Day 5 Participants will provide a urine sample (drug toxicology), and a one vial blood sample (β -endorphin, hormone levels). Participants will then complete a series of assessments (**Table 1**) and receive a single oral dose of yohimbine or yohimbine-matched placebo. Fifteen minutes later, participants will administer a dose of oxytocin or oxytocin-matched placebo (40 IU, 4 sprays per nostril), after 30 min the first sample of saliva (cortisol and oxytocin) will be collected and the cue-reactivity will begin (112). Cue-Reactivity (CR) Task will be administered in a similar manner to other published studies (72, 73) for individuals with OUD with cues selected based on patients' drug experience. To measure cue-induced opioid craving, participants will a view images of neutral stimuli and then of opioid drug use (24). Participants will rate their craving via drug visual analog scale (VAS) and the second sample of saliva cortisol will be collected (45 min later). Vital signs will be monitored during the entire procedure. Participants will then complete Post-Cue measures, will have their vital signs measured and conduct the last sample of saliva.

Visit 4 (Laboratory Session II) – Day 7 Participants will come back after two days. The procedure will be similar to Visit 3 but they will receive the opposite condition (yohimbine or yohimbine-matched placebo).

A two-day washout period will occur followed by initiation of the opposite intranasal medication condition (i.e. oxytocin and oxytocin-matched placebo) to be administered for one week starting at day 9.

Visit 5 (Laboratory Session III) – Day 14 Participants will complete the lab procedures as described in Visit 3 and 4, however, this time will be administered the opposite oxytocin condition (i.e. oxytocin or oxytocin-matched placebo). Participants will also receive yohimbine or yohimbine-matched placebo (counterbalanced).

Visit 6 (Laboratory Session IV) – Day 17 Participants will come back after two days. The procedures will be completed as described in Visits 3-5, but they will receive the opposite condition (yohimbine or yohimbine-matched placebo).

Visit 7 (follow-up) – Day 20 After three days, participants will come to the lab for the final assessments (Table 1).

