The ITT analysis was suitable for this crossover design ³ as the placebo condition was treated identically to the active drug condition (route, administration and laboratory procedures). Distributional characteristics of outcome measures were examined to evaluate similarity to the normal distribution. detailed descriptive analysis of demographics, substance use, and clinical characteristics. The cortisol had a kurtosis in excess of four; consequently, an outlier analysis was performed and a total of 5 outliers falling outside of ±3 interguartile range were Winsorized as recommended ⁴. Comparisons with these characteristics, in relation to enrolled versus completer status, were performed using *t*-tests to analyze continuous variables (age) and χ^2 for categorical variables (sex, race, medication status). Attrition rates between the screening visit and follow-up visit were examined descriptively to assess for potential bias. In addition, a logistic regression was performed to test for possible bias due to period (placebo first, then oxytocin and oxytocin first, then placebo) or medication carryover (placebo and oxytocin), as done in our prior cross-over trial ⁵. This study tested the feasibility of the combined study design, the safety and tolerability of IN oxytocin and yohimbine, and the potential value of testing IN oxytocin as adjunct therapy in an appropriately-powered larger RCT. In selecting a target sample size, we balanced power considerations and feasibility given the preliminary nature of this trial. Because of the within-subjects design, power to test the effects of the study drug was optimized for this modest sample size. For the safety and tolerability outcomes (primary) adverse events, difference was detected based on a

judgement concerning the minimal effect, which has clinical relevance in the management of patients. In a noninferiority trial, the exact sample size could not be fixed in advance because it depends upon the chosen stopping guidelines ⁶.

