Outcomes: Primary (craving) and secondary (safety and tolerability) outcomes were assessed in realtime in the laboratory. Seven-day oxytocin administration was compared to the oxytocin-matched placebo condition during the CR procedure, in which noradrenergic activation produced by yohimbine or yohimbinematched placebo condition (2X2 design) was measured. We used Generalized Linear Model (GLM) with modelbased estimator in the covariance matrix, with medication (oxytocin/placebo) and noradrenergic activation (yohimbine/placebo) as within-subject factors. The model was specified to evaluate the effect of drug (oxytocin/placebo) by noradrenergic (vohimbine/placebo) interaction, main effect of the drug, and main effect of noradrenergic activation. Craving was assessed using the DDQ with time coded as: t_0 =relaxation, t_1 =interaction with drug paraphernalia/opioid auditory cues and t_2 =opioid use video. Safety and tolerability were assessed using: SBP, DBP, HR (vital signs), HAM-A and STAI (anxiety). The STAI y1 (state) was included as an additional safety measure for anxiety to ensure participants were not experiencing acute symptoms of anxiety within the laboratory. The STAI y2 (trait) was inserted as a covariate in the model to control for baseline anxiety level, along with stress (PSS), HPA (cortisol), and noradrenergic response (α -amylase). Time at laboratory sessions was coded as: t_0 =baseline, t_{45min} =45-min after yohimbine administration, and t_{90min} =post cue-exposure to specifically evaluate the contribution of each laboratory procedure (vohimbine and CR). Withdrawal symptoms (COWS) and AEs were assessed at specific timepoints: t_0 =pre-laboratory and t_1 =post-laboratory procedures.

Other outcomes (safety and tolerability) were measured retrospectively during the one-week outpatient setting and included the: COWS (withdrawal), anxiety (HAM-A and STAI), stress (PSS), depression (HAM-D) and AEs. The other outcomes were analyzed using ANOVA test and the number of AEs via a χ^2 test. For missing data approach, we first categorized missing data as missing completely at random (MCAR), missing at random (MAR) or missing not at random (MNAR)⁷. Analysis with GLM (using all available pairs of data to model missing values with maximum likelihood estimation) was deemed suitable for our analyses because no systematic differences existed between participants with missing data and those with complete data (MCAR)⁸.

Missing data reporting ⁹

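### The SAP's crossover-bias check mislabels its terms and names no response, so the plan specifies no valid test of period or carryover for craving or the continuous safety scores

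*SAP*

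**What the plan says.** The whole description of the check is one sentence in the SAP, Statistical analysis. It reports a logistic regression and gives this aim: "test for possible bias due to period (placebo first, then oxytocin and oxytocin first, then placebo) or medication carryover (placebo and oxytocin"). For the method it points to the group's earlier crossover study. It names no response variable, no first-versus-second-course factor and no previous-treatment term. The sentence before it concerns dropout: "Attrition rates between the screening visit and follow-up visit were examined descriptively to assess for potential bias".

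The craving outcome is described under Outcomes: "Craving was assessed using the DDQ with time coded as" three laboratory stages. Its generalized linear model has medication and yohimbine as within-subject factors, their interaction, and covariates (trait anxiety, perceived stress, cortisol, alpha-amylase). Neither period nor sequence appears. Results are to be given as means, SDs and Cohen's d, and no cut-point is defined for DDQ, blood pressure, heart rate, HAM-A or STAI.

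Under Missing data reporting, the SAP counts 16 participants who received both spray conditions and 4 who received one. The number in each sequence is not given.

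On timing, Protocol Part III section 3 states: "A two-day washout period will occur followed by initiation of the opposite intranasal medication condition". The oxytocin paragraph of the same section says that "the pharmacological effect of oxytocin may extend from the transient kinetic effects". The section also provides for earlier completers to be re-enrolled in the opposite condition, without stating how long after their first course.

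**The concern.** In a two-sequence, two-course crossover, period and carryover are the two standard threats to the within-person drug comparison. This sentence is the only place where the plan addresses them. If its terms do not correspond to those effects, the comparison has no stated safeguard.

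The question is relevant to this trial. The protocol itself allows that oxytocin's action may outlast its kinetics, and the washout is two days. The second outpatient week is an outcome window in its own right (withdrawal, anxiety, stress, depression, adverse events) and starts directly after that washout. The design also changed from between-subjects to crossover during the trial, so for re-enrolled completers the second course may differ in calendar time and circumstances.

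**Working it through.** The documents give no figure for this check, so there is none to reproduce. The working is design algebra followed by power.

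**1. What each listed term can estimate.** Let τ be the oxytocin effect, π the shift from course 1 to course 2, and λ the carryover of oxytocin into a following placebo course. Leaving out the common mean, the expected scores are:

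| Sequence | Course 1 | Course 2 |
|---|---|---|
| Placebo, then oxytocin | 0 | τ + π |
| Oxytocin, then placebo | τ | π + λ |

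- Sequence contrast (the SAP's period), in participant means: (τ + π + λ)/2 − (τ + π)/2 = λ/2. π cancels, so this contrast carries no information on period. It equals half of a carryover confined to course 2.
- Treatment contrast (the SAP's carryover), oxytocin minus placebo: τ + π in the first sequence and τ − π − λ in the second. With equal sequences the average is τ − λ/2. This is the drug effect, reduced by carryover, and is not a test of carryover.
- Period contrast, course 2 minus course 1 averaged over sequences: [(τ + π) + (π + λ − τ)]/2 = π + λ/2. The SAP lists no such term.

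**2. Numerical check.** Assumptions: n = 16 split 8 + 8, within-person correlation ρ = 0.3 to 0.7, two-sided 5%, effects in SDs of a single-course score. Simulation used 20,000 trials per scenario.

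| Truth | Contrast | Rejection rate |
|---|---|---|
| π = 0.5 SD, no drug effect | Sequence (SAP's period) | about 5% |
| π = 0.5 SD, no drug effect | True course 1 vs course 2 | 35% to 67% |
| τ = −0.5 SD, λ = 0 | Treatment (SAP's carryover) | 35% to 68% |
| τ = −0.5 SD, λ = −0.5 SD | Treatment (SAP's carryover) | 12% to 20% |

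The contrast labelled period rejects at its false-positive rate whatever the period shift. The contrast labelled carryover rejects more often when there is none. In the last row the estimated drug effect is halved: −0.50 + 0.25 = −0.25 SD.

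**3. Power of a correctly specified carryover test.**
- SD of a participant's two-course mean = √((1 + ρ)/2): √0.65 = 0.806 at ρ = 0.3 and √0.85 = 0.922 at ρ = 0.7.
- SE of the sequence difference = that SD × √(1/8 + 1/8) = 0.403 to 0.461.
- Noncentrality for carryover L = (L/2)/SE. At L = 0.5 SD: 0.25/0.403 = 0.62 and 0.25/0.461 = 0.54. At L = 1.0 SD: 1.24 and 1.08.
- Power with 14 df: 8.9% and 8.0% at 0.5 SD; 21% and 17% at 1.0 SD.
- 95% CI half-width for L = 2 × t(0.975, 14) × SE = 2 × 2.145 × 0.403 = 1.73 SD, and 2 × 2.145 × 0.461 = 1.98 SD.

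The scale matters. Treating 0.5 or 1.0 SD as a difference in participant means, in SDs of those means, gives 15% and 46% power and a half-width of 2.145 × 0.5 = 1.07. Those figures overstate what the test can do, because carryover enters only one of the two courses.

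**4. If the sequences are unequal.** With an assumed 11 and 5, a 0.5 SD period shift biases a drug estimate without a period term by 0.5 × (11 − 5)/16 = 0.19 SD. Adding period removes the bias. With 8 and 8 it is zero.

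**The case against.** The strongest reply is that the SAP does list the contrast that usually detects carryover. Placebo-first versus oxytocin-first is the sequence contrast, and it merely carries the wrong name. Sequence is itself binary, so a logistic model of sequence on craving would come close to the usual test. The method is also given by reference to the group's earlier crossover trial, whose details are not in these documents. This much stands: a reader might infer that the check could not have detected carryover under any model, and the text does not support that. The response is unstated. It could be completion (the preceding sentence is about attrition), an adverse-event indicator, or sequence itself. What can be said is that the SAP specifies no valid test for the craving and continuous safety scores.

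A reader might also infer that the SAP declares period and carryover ruled out. It does not: it reports no result from this check and draws no conclusion.

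Third, the risk to the craving sessions is limited. First-course dosing ends around day 7 and the next laboratory session is on day 14, about 7 days later. The protocol gives a serum half-life of 3 to 17 minutes and describes longer action only as a possibility. Order is counterbalanced, and with equal sequences a period shift cancels from the drug contrast. This also stands, with two limits: the actual sequence split is not given, and the second outpatient week does not have the 7-day gap.

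**Conclusion.** The point holds for the text as written. The SAP's period term is sequence, its carryover term is current treatment, the logistic model has no stated response, and the craving model has neither period nor sequence. The documents do not show that carryover or period bias occurred, and they should not be read that way.

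The low power and wide interval rest on an 8 + 8 split and ρ of 0.3 to 0.7, neither of which the documents give. Across that range a non-significant carryover test at n = 16 could not exclude a carryover larger than 1 SD. The possible bias from omitting period depends on the split: zero if equal, 0.19 SD in the 11/5 example.

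Because the SAP presents the trial as preliminary and exposure of the craving sessions is limited, this is a correction to make before the crossover comparison is relied on. It does not invalidate the trial.

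**What to change.** - Do not use this logistic regression as evidence on period or carryover for DDQ or the continuous safety scores. If it was an attrition or adverse-event model, name its response and describe it as that.
- For DDQ and each continuous safety score, fit a linear mixed model that includes period (course 1 versus course 2) and sequence. Report both estimates with 95% CIs.
- State that the sequence difference in participant means is half of a carryover confined to course 2.
- Fit these terms in the 16 participants who received both courses, and report the number in each sequence. Identify re-enrolled completers separately, with the time between their courses, since course 1 versus course 2 may mean something different for them.
- Use the 4 single-condition participants only in a sensitivity estimate of oxytocin versus placebo from first courses alone, labelled as imprecise.
- Do not conclude that there was no carryover from p>0.05.

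The cost is a revised SAP paragraph and a few extra model runs on data already collected. The carryover and first-course estimates will be imprecise, and the report should say so.

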- Current substance disorder other than marijuana, nicotine and caffeine as assessed by self-report and urine toxicology screen at baseline;
- Current use of medications that may interact with study medications;
- History of hypersensitivity to study medications;
- Clinically significant electrolyte abnormalities, current rhinitis or use of vasoconstricting medications or prostaglandins.

NOTE: the exclusion criteria are based in reducing participants' safety.

Participants need to speak English and be able to understand informed consent and questionnaires in English which will be written exclusively at an 8th grade level.

One hundred individuals receiving buprenorphine/naloxone or methadone as opioid replacement therapy (ORT) will be screened, 80 will be randomized, with 50 expected to complete the study. Potentially eligible participants will be invited for an in-person screening, where they will provide written informed consent and undergo a physical examination in the NEW Clinical Laboratory Core (CLC).

The **sample size estimate** is based on recent findings reporting that baseline levels of stress significantly predicted oxytocin effects on cue-induced craving (Mitchell et al., *J Addict Med*, 2016). Effect sizes were calculated based on a between-subjects in oxytocin study with alcohol related responses (Pedersn et al., *ACER*, 2013). The estimate of opioid craving (measured by the OCQ) were calculated from the *M* and the *SD* of alcohol-related outcomes: oxytocin was superior to placebo in reducing alcohol withdrawal (*i.e.* less lorazepam required to complete detoxification: 3.4 mg±4.7, vs. 16.5 mg±4.4, p<0.01), lower mean CIWA scores (4.3 mg±2.3 vs. 11.8 mg±0.4, p<0.01). We estimated that with a standard threshold, α = 0.05, for med-large effect (f = 0.35), two group independent variable and three covariates in ANCOVA, the *N* is 67 to detect 0.80 power. With an additional 0.20 to account for attrition [N = 50 (completers) + 13 = 80 (enrolled)]. The estimated power at N = 67, with the addition of an interaction term (for Aim 2) would be = 0.63. Therefore, the calculated sample size is well powered to address the hypothesis of the main medication effect (Aim 1) and of the interaction effect with stress and anxiety (Aim 2).

5. Recruitment Methods

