- 1. Amount of missing data in the dataset:
 - a. Oxytocin condition: 10% did not receive either oxytocin or placebo condition (within subject, *n*=16; between subject, *n*=4)
 - b. Yohimbine condition: 11.12% did not receive yohimbine condition (yohimbine, *n*=14; placebo, *n*=16; no yohimbine, *n*=4):

- 2. Reason for missing:
 - a. Oxytocin condition: change from between subject to within subject design
 - b. Yohimbine condition: safety concerns due to past history of cardiovascular disease and/or current hypertension (*n*=3), stroke (*n*=1)

3. Consequences:

- a. *Oxytocin condition*: no differences between participants with and without missing values except there were no subject taking methadone in the subjects with missing values.
- b. *Yohimbine condition*: no differences between participants with and without missing values except there were cardiovascular concerns in the subjects with missing values.
- 4. *Method*: GLM with MNAR using all available pairs of data to model missing values with maximum likelihood estimation
- 5. Software: IBM SPSS Statistics for Windows, version 29 (IBM Corp., Armonk, NY, USA)

All statistical analyses were performed after participants had completed their follow-up visits and the study database had been locked. The results were presented using summary statistics: number of subjects (n); mean (M); standard deviation (SD) or frequency distributions (%) and effect size was reported as Cohen's d.

All statistical procedures were performed by IBM SPSS Statistics for Windows, version 29 (IBM Corp., Armonk, NY, USA), and GraphPad Prism (v.10) was used to generate figures (La Jolla, CA, USA). All statistical tests were two-tailed, and statistical significance was accepted if an alpha value p<.05 was obtained.

References

1. FDA. Changes or modifications during the conduct of a clinical investigation; final guidance for industry and CDRH staff. 20012001.

Schulz K, Altman D, Moher D. Consolidated Standards of Reporting Trials Group CONSORT
2010 Statement: Updated Guidelines for Reporting Parallel Group Randomised Trials. Bmj.
2010;340:c332.

4. Tukey JW. The future of data analysis. The annals of mathematical statistics. 1962;33(1):1-67.

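### The protocol's size and power statement (N = 67, 80 randomised, 50 completers) was not redone for the crossover or for the 20 participants in the dataset, and the SAP gives no target, shortfall or power in its place

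*SAP*

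**What the plan says.** Protocol Part III, section 4 (Participant Population) holds the only sample size calculation in the documents. It takes α = 0.05 and is set up "for med-large effect (f = 0.35), two group independent variable and three covariates in ANCOVA", giving N = 67 for 0.80 power. It expects 100 people screened, of whom "80 will be randomized, with 50 expected to complete the study". It states 0.63 power at N = 67 once an interaction term is added for Aim 2 (baseline stress), and concludes that the size gives good power for Aims 1 and 2.

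Section 3 of the same Part already describes a within-subject design. The SAP (Study design, setting and approval) explains that the trial began as between-subjects and became a crossover after the pandemic, to speed recruitment.

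On size, the SAP (Statistical analysis) says: "In selecting a target sample size, we balanced power considerations and feasibility given the preliminary nature of this trial". It adds: "Because of the within-subjects design, power to test the effects of the study drug was optimized for this modest sample size". It names no target number, effect size, within-person correlation or power, and later in the same paragraph says the exact size could not be fixed in advance.

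The counts appear only under Missing data reporting. Item 1a gives "within subject, *n*=16; between subject, *n*=4" for the sprays and item 1b gives "yohimbine, *n*=14; placebo, *n*=16; no yohimbine, *n*=4" for the capsules. The SAP's model for the 2×2 design tests the oxytocin-by-yohimbine interaction and the two main effects.

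**The concern.** The protocol's calculation compares two separate groups; the analysis compares sessions within people. Its 50 completers also differ from the 16 + 4 = 20 participants in the dataset, which is 20/50 = 40% of that number. Neither document bridges the gap. The SAP describes a selected target without saying what it was, and its power sentence speaks of the study drug's effects without saying which.

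The distinction matters because a 2×2 crossover does not serve all its contrasts equally. An oxytocin effect averaged over both capsule conditions is estimated precisely. The effect after yohimbine alone (Aim 1) is less precise, and the interaction, a difference of differences, is the least precise. The trial's central question is about stress-induced craving, so it rests on the weaker contrasts. A reader holding the protocol's favourable power conclusion and the SAP's sentence could take a non-significant interaction as evidence that oxytocin acts independently of stress.

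**Working it through.** **1. The protocol's figure.** Inputs from Protocol Part III, section 4: f = 0.35, two groups, three covariates, α = 0.05. Noncentral F with 1 and N − 5 degrees of freedom and λ = f²N. At N = 67, λ = 0.1225 × 67 = 8.21 and power = 0.805, so the stated N reproduces. The same test at 50 has power 0.68.

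**2. The counts.** Item 1a: 16 + 4 = 20 participants. Four missing spray conditions out of 2 × 20 = 40 is 10%, as the SAP states. If item 1b counts persons on the same base of 20, the overlap of both sprays (16) and yohimbine (14) is at least 16 + 14 − 20 = 10 and at most 14. This is an inference. The stated 11.12% fits 4/36 = 11.11%, with 36 = 16 × 2 + 4 spray conditions delivered. Item 2b gives reasons for 3 + 1 = 4 people without yohimbine, which would leave 16 rather than 14 out of 20. So n = 16 is shown as well.

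**3. Contrasts.** Assumptions:
- d = 2f = 0.70, scaled to a session SD of 1;
- equal correlation ρ between sessions (not in the documents);
- two-sided 0.05, as in the SAP;
- oxytocin acts after yohimbine only, unless stated otherwise.

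Standardised effects for a one-sample noncentral t on n people:
- Aim 1 contrast (oxytocin minus placebo after yohimbine): variance 2(1 − ρ), effect 0.70/√(2(1 − ρ)).
- Interaction: variance 4(1 − ρ), effect 0.70/(2√(1 − ρ)).
- Main effect, d = 0.70 under both capsules: variance 1 − ρ, effect 0.70/√(1 − ρ).
- Main effect if oxytocin acts after yohimbine only: 0.35/√(1 − ρ), the same as the interaction.

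Example at ρ = 0.5: 0.70 for the Aim 1 contrast, 0.495 for the interaction and 0.99 for the full main effect.

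| Contrast | n | ρ = 0.3 | ρ = 0.5 | ρ = 0.7 | ρ = 0.8 |
|---|---|---|---|---|---|
| Interaction | 10 | 0.22 | 0.29 | 0.44 | 0.60 |
| Interaction | 14 | 0.31 | 0.40 | 0.60 | 0.77 |
| Interaction | 16 | 0.35 | 0.46 | 0.67 | 0.83 |
| Aim 1 contrast | 10 | 0.39 | 0.51 | 0.72 | 0.87 |
| Aim 1 contrast | 14 | 0.54 | 0.68 | 0.88 | 0.97 |
| Aim 1 contrast | 16 | 0.60 | 0.74 | 0.92 | 0.98 |
| Main effect, d = 0.70 under both | 16 | 0.88 | 0.96 | 1.00 | 1.00 |

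At ρ = 0 the interaction has 0.17 to 0.23 for n = 10 to 14. With 50 people completing all four sessions it would have 0.83, 0.93 and 0.99 at ρ = 0.3, 0.5 and 0.7.

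**4. Is the relative claim true?** Compare 14 people in the crossover with 14 in a design with oxytocin between and yohimbine within subjects (an assumption about the starting design). The interaction variance falls from 8(1 − ρ)/n to 4(1 − ρ)/n. Interaction power at ρ = 0.3, 0.5 and 0.7 is 0.31, 0.40 and 0.60, against 0.18, 0.23 and 0.34. The Aim 1 contrast has 0.54, 0.68 and 0.88, against 0.23 throughout. The crossover helps for both.

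**The case against.** The SAP's power sentence is relative, and step 4 bears it out, for the stress-specific contrasts too. That stands: the sentence is not false, but it leaves absolute power unstated.

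The same SAP paragraph calls the sample modest and the trial preliminary, and looks ahead to a larger, adequately powered trial. The design change is disclosed and the counts are printed. This tempers the harm, but none of it tells the reader the planned number, the gap, or which contrast is weak.

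Power computed after database lock adds little beyond a confidence interval. That is fair, and a minimum detectable effect or an interval for each contrast would do as well.

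Four stronger readings are tempting but unsupported:
- That 0.80 was promised for the oxytocin-by-yohimbine test. It belongs to the two-group medication effect at N = 67, and the only interaction power stated is 0.63, for baseline stress. Aim 1 is the contrast after yohimbine, not the interaction.
- That enrolment ended at 20. The count describes the dataset, and the SAP separately compares enrolled people with completers.
- That a quarter of the randomisation target was reached. The number randomised is not given.
- That a non-significant interaction was the most likely result. At ρ = 0.7 and n = 14, power is 0.60, so significance would be the likelier outcome.

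**Conclusion.** The concern holds as a gap between the stated and delivered size and power. The protocol's 0.80 and its conclusion of good power describe a between-group comparison at N = 67, not a crossover dataset of 20, and the SAP supplies no replacement.

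With the planned effect confined to yohimbine sessions and 10 to 14 informative participants, interaction power stays below 0.80 for every correlation considered from 0 to 0.8 (0.17 to 0.77). The Aim 1 contrast is below 0.80 up to a correlation of 0.5 and can exceed it at 0.7. A main effect of d = 0.70 under both capsules is well covered at n = 16 for correlations of 0.3 or more, provided all 16 have the four sessions.

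These figures rest on an assumed correlation, equal correlation between sessions, and an overlap inferred from counts whose denominators are unclear. If all 16 crossover participants had four sessions, interaction power reaches 0.83 at a correlation of 0.8 but is still 0.67 at 0.7.

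**What to change.** In the SAP's Statistical analysis section:

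- State the planned 80 randomised and 50 completers, the 20 participants in the dataset (16 with both sprays, 4 with one), and how many had all four sessions.
- Replace the power sentence with one saying that the crossover improves power relative to a between-subjects design of the same size.
- Give power or minimum detectable effect over a stated range of correlations, separately for the oxytocin main effect, the Aim 1 contrast after yohimbine, and the interaction. Report a confidence interval for each alongside.
- State that the protocol's 0.80 and its conclusion of good power do not carry over to the analysed sample.
- State that a non-significant interaction is inconclusive and does not show that oxytocin's effect is independent of stress.

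Cost: a few sentences in the SAP and report, plus one short calculation. The downside is a less favourable stated power. No more patients are needed.
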